4.6.3.1.2. Hypoglycemic Events Derived from CGM

Level 2, Level 2 ending with BG value ≥ 70 mg/dL, and Level 1 or Level 2 hypoglycemic events collected from the sponsor provided CGM are defined in [Appendix 6](#), Section 6.6.2. The analysis for incidence, event rate and duration are described in the table below. All data are included in the analysis. Missing data will be handled as described in [Appendix 6](#).

Endpoint	CGM Session	Statistical Method
Event rate of Level 1 or Level 2 hypoglycemic events (events/participant/year): 
 • 24-hour 	Baseline, 0-4, 8-12, 22-26, 48-52, 0-52 weeks (combine all sessions during treatment period), post-treatment period	Negative binomial regression with treatment and baseline HbA1c as covariates, log (exposure/365.25 days) as the offset in the model.

Endpoint	CGM Session	Statistical Method
Event rate of Level 2 hypoglycemic events (events/participant/year): 
 • 24-hour 	Baseline, 0-4, 8-12, 22-26, 48-52, 0-52 weeks (combine all sessions during treatment period), post-treatment period	Negative binomial regression with treatment and baseline HbA1c as covariates, log (exposure/365.25 days) as the offset in the model. If the number of events is too small to run the negative binomial regression, exposure adjusted rate calculated by total number of events divided by total exposure for individual participants will be provided and the empirical method (see Appendix 9 [Section 6.9] for details) will be used for treatment comparison.
Event rate of Level 2 hypoglycemic events ending with ≥ 70 mg/dL (events/participant/year): 
 • 24-hour 	Baseline, 0-4, 8-12, 22-26, 48-52, 0-52 weeks (combine all sessions during treatment period), post-treatment period	Negative binomial regression with treatment and baseline HbA1c as covariates, log (exposure/365.25 days) as the offset in the model. If the number of events is too small to run the negative binomial regression, exposure adjusted rate calculated by total number of events divided by total exposure for individual participants will be provided and the empirical method (see Appendix 9 [Section 6.9] for details) will be used for treatment comparison.
Incidence of Level 1 or Level 2 hypoglycemic events: 
 • 24-hour 	Baseline, 0-4, 8-12, 22-26, 48-52, 0-52 weeks (combine all sessions during treatment period), post-treatment period	Logistic regression with treatment and baseline HbA1c as covariates. The total number of episodes, number of episodes that includes Level 2 hypoglycemia episodes, and number of episodes that include glucose readings <54 mg/dL (3.0 mmol/L) but no Level 2 hypoglycemia episodes will be summarized for each CGM session.
Incidence of Level 2 hypoglycemic events: 
 • 24-hour 	Baseline, 0-4, 8-12, 22-26, 48-52, 0-52 weeks (combine all sessions during treatment period), post-treatment period	Logistic regression with treatment and baseline HbA1c as covariates.

Endpoint	CGM Session	Statistical Method
Incidence of Level 2 hypoglycemic events ending with ≥ 70 mg/dL: • 24-hour	Baseline, 0-4, 8-12, 22-26, 48-52, 0-52 weeks (combine all sessions during treatment period), post-treatment period	Logistic regression with treatment and baseline HbA1c as covariates.
Duration of Level 1 or Level 2 hypoglycemic events: • 24-hour	Baseline, 0-4, 8-12, 22-26, 48-52, 0-52 weeks (combine all sessions during treatment period), post-treatment period	The MMRM model will include treatment, strata (country, baseline HbA1c stratum ($<8.0\%$, $\geq 8.0\%$)), GLP-1 RA treatment at randomization, and SU use at randomization), time and treatment-by-time interaction as fixed effects, and baseline duration as a covariate. For 0-52 weeks: ANCOVA model will include treatment, strata and baseline duration. For Baseline and post-treatment period: ANOVA models only include treatment.
Duration of Level 2 hypoglycemic events: • 24-hour	Baseline, 0-4, 8-12, 22-26, 48-52, 0-52 weeks, post-treatment period	Same models as for Level 1 or Level 2 hypoglycemic events. A listing will be provided for participants with Level 2 hypoglycemia episodes lasting >360 minutes
Duration of Level 2 hypoglycemic events ending with $BG \geq 70$ mg/dL: • 24-hour	Baseline, 0-4, 8-12, 22-26, 48-52, 0-52 weeks, post-treatment period	Same models as for Level 1 or Level 2 hypoglycemic events.

Abbreviations: HbA1c = hemoglobin A1c.

Note: The hypoglycemic yearly rate during defined period is calculated by number of hypoglycemic events within the period/number of days patient at risk within the period * 365.25. The hypoglycemia incidence during defined period indicates if the patient has at least 1 hypoglycemic event within the period (Yes/No).

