1.2. Study Design

- This is a Phase 3, parallel-design, open-label, randomized control study to evaluate the efficacy and safety of LY3209590 administered once-weekly compared to insulin degludec administered daily.
- The study includes a 3-week screening and lead-in period, a 52-week treatment period, and a safety follow-up period approximately 5 weeks after the last visit in the treatment period.
- Assignment to treatment groups will be determined by an interactive web-response system (IWRS). Participants will be randomly assigned to 1 of the 2 treatment groups in 1:1 ratio (LY3209590: insulin degludec) at Visit 3 (Week 0). The number of participants in each subpopulation of participants using or not using GLP-1 RA will be approximately 50% of the study population with balanced treatment assignment. Stratification will be by country, HbA1c stratum at Visit 1 (Week -3) (<8.0%, ≥8.0%), sulfonylurea use at randomization, and GLP-1 RA use at randomization, regardless of oral or injectable administration.
- Rescue therapy will be considered during the treatment period if the participants meet the protocol criteria of severe, persistent hyperglycemia.
- If study intervention is permanently discontinued, the participant will be encouraged to continue participation in the study for continued monitoring. Both efficacy (including HbA1c) and safety data will continue to be collected per the schedule of activities in the protocol.
- Participants will collect blinded CGM for 2 weeks prior to Visit 3 (Week 0), for 4 weeks prior to Visit 7 (Week 4), Visit 15 (Week 12), Visit 24 (Week 26), Visit 31 (Week 52), and for 4 weeks after Visit 31 (Week 52). Dexcom G6 system provides readings every 5 minutes. In China, instead of the Dexcom G6 system, the Libre Freestyle H system which provides readings every 15 minutes will be used. Main analyses for CGM measurements will be conducted based on data from the Dexcom G6 system.

2. Statistical Hypotheses

Primary Hypothesis

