CGM parameters (treatment regimen estimand)	The baseline will be derived from the data collected during CGM session prior to the first dose date of study treatment. Multiple imputation will be used to impute missing observations at baseline.	The CGM session prior to Visit 24 (Week 26) and Visit 31 (Week 52) in EAS1 Multiple imputation approach will be used to impute missing observations at Visit 24 (Week 26) and Visit 31 (Week 52).
CGM parameters (efficacy estimand)	The baseline will be derived from the data collected during CGM session prior to the first dose date of study treatment.	The CGM sessions prior to Visit 7, 15, 24, and 31 (Weeks 4, 12, 26, and 52) in EAS2 for MMRM

Analysis	Baseline Observations	Post-Baseline Observations
Insulin dose during the treatment period	N/A	
All scheduled visits between Visit 3 and Visit 31 in EAS2 for MMRM.
 
The averages of weekly basal insulin doses between visits for individual participants will be used in the analysis. (Section 4.4.2.1)

Fasting glucose by SMBG	
The baseline period is the lead-in period up to the day of first dose of study treatment. Baseline will be derived as the average of all fasting glucose measurements between V2 date and the first dose date.
 
Multiple imputation will be used to impute missing observations at baseline for treatment regimen estimand.
	
All available data after the day of first dose of study treatment up to Week 52 (Visit 31) in EAS2 for MMRM (efficacy estimand).
 
Values at each visit will be derived as average of all fasting glucose measurements from the day post prior visit up to the day of next visit.
 
Data at Week 26 (Visit 24) and Week 52 (Visit 31) in EAS1 for ANCOVA with multiple imputation for missing data (treatment regimen estimand).

Fasting serum glucose	
The baseline is the last non-missing assessment prior to or on the day of the first dose of study treatment.
 
Multiple imputation will be used to impute missing observations at baseline for treatment regimen estimand.
	
All scheduled visits after the day of first dose up to Week 52 (Visit 31) in EAS2 for MMRM (efficacy estimand)
 
Planned measurements at scheduled visits will be included.
 
Data at Week 26 (Visit 24) and Week 52 (Visit 31) in EAS1 for ANCOVA with multiple imputation for missing data (treatment regimen estimand)
 
.

Analysis	Baseline Observations	Post-Baseline Observations

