6.6. Appendix 6: Derivation of CGM Variables

Blinded CGM will be worn by participants at the following designated weeks:

- Two weeks in screening/lead-in period with the data download at Visit 3 (Week 0),
- Four weeks after the initiation of study treatment with the data download at Visit 7 (Week 4),
- Four weeks from V7 (Week 4) with the data download at Visit 11 (Week 8) (only for sites in Japan),
- Four weeks near the end of weekly titration period with the data download at Visit 15 (Week 12),
- Four weeks near the end of half year treatment with the data download at Visit 24 (Week 26),
- Four weeks near the primary endpoint with the data download at Visit 31 (Week 52), and
- Four weeks after the end of study treatment period with the data download at Visit 802 (Week 57).

Dexcom G6 system will be used in all countries to collect CGM data except China. In China, Libre Freestyle H system will be used instead.

Linear interpolation will be used to impute the missing glucose readings during intervals >7 minutes and ≤ 15 minutes. Missing data will be imputed at a 5-minute interval using the BG value before and the one after the interval.

For example, the BG reading before the interval is 50 mg/dL at time 100 min, and the BG reading after interval is 70 at time 115 min, then the missing records will be imputed as:

- at time 105 min, BG reading= $50+5*(70-50)/(115-100)=56.7$, and
- at time 110 min, BG reading= $50+10*(70-50)/(115-100)=63.3$.

Glucose reading intervals >15 minutes will be treated as missing data and not be counted in the length of the analysis periods. Since the Libre Freestyle H system normally provides readings every 15 minutes, the linear interpolation missing data imputation will not be performed.

As shown in the table below, all the CGM derivations are based on the data from valid CGM periods of a day and sessions unless otherwise specified.

Minimum Data Available to Define a Valid Period of the Day and CGM Session

Period	Definition of Valid Period	Definition of Valid CGM Session
Valid CGM Day (00:00-23:59)	$\geq 70\%$ of expected values available (≥ 202 of 288 values for Dexcom G6 system; ≥ 68 of 96 values for Libre Freestyle H system)	≥ 3 valid CGM days within a visit define a valid CGM visit. A valid CGM session only includes valid CGM visits.

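### The CGM hypoglycemia event-rate models omit each participant's own baseline CGM hypoglycemia: a modest precision and consistency point, not a source of bias

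*SAP*

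**What the plan says.** SAP 4.6.3.1.2 lists three CGM event-rate endpoints: Level 1 or Level 2, Level 2, and Level 2 ending at 70 mg/dL or above. Each uses "Negative binomial regression with treatment and baseline HbA1c as covariates, log (exposure/365.25 days) as the offset in the model". The three matching incidence endpoints use "Logistic regression with treatment and baseline HbA1c as covariates". The sessions analyzed are "Baseline, 0-4, 8-12, 22-26, 48-52, 0-52 weeks (combine all sessions during treatment period), post-treatment period", so the baseline session is analyzed as an outcome in its own right.

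The baseline session is two weeks of blinded CGM ending at Visit 3 (SAP 1.2 and Appendix 6). For CGM parameters generally, SAP 4.1 says: "The baseline will be derived from the data collected during CGM session prior to the first dose date of study treatment".

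Other CGM models do use a baseline CGM value. For event duration, in the same table, the on-treatment MMRM includes baseline duration and the strata, and "For 0-52 weeks: ANCOVA model will include treatment, strata and baseline duration". The time-in-range and time-below-range models (SAP 4.4.2.1 and 4.4.2.2) follow the primary-type model, which includes the baseline of the dependent variable. The SAP gives no reason for treating the rate models differently.

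**The concern.** A participant's pre-treatment CGM lows measure directly how prone that person is to going low. HbA1c does so only indirectly: the protocol (4.2) describes it as reflecting cumulative glucose over the preceding 2 to 3 months. A prognostic baseline value that has been collected but is left out of a count model leaves between-participant variation unexplained.

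At stake is the width of the interval for the CGM rate ratio. The trial is open-label and reported hypoglycemia comes from the e-diary. The CGM readings are hidden from participant and investigator (protocol 8.1.1.2), so this comparison depends least on who reports what, and its precision deserves some care.

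**Working it through.** The plan states no event rate, dispersion, correlation or power for CGM hypoglycemia events, so there is no figure to reproduce. Every rate and correlation below is an assumption.

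**1. Models side by side (SAP)**

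| Endpoint | Terms besides treatment |
|---|---|
| CGM event rate, 3 rows | baseline HbA1c, exposure offset |
| CGM incidence, 3 rows | baseline HbA1c |
| CGM duration, on treatment | strata, baseline duration (plus time terms in the MMRM) |
| CGM duration, baseline and post-treatment | none |
| CGM time in ranges (4.4.2.1) | strata, HbA1c stratum, own baseline |

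The inconsistency therefore concerns the on-treatment rows. For the post-treatment rows, the case for a baseline term rests on precision alone.

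**2. Linear benchmark.** In a linear model, a covariate with correlation r multiplies residual variance by 1 − r². For r = 0.2, 0.35 and 0.5 this gives 0.96, 0.88 and 0.75. The equivalent sample gains, 1/(1 − r²) − 1, are 4%, 14% and 33%. These do not carry over to negative binomial or logistic models, and a short baseline window gives little information when events are rare.

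**3. Simulation of the rate model with baseline count.** Settings: 754 participants, 377 per arm (completers in SAP section 5; an upper bound here, because the main CGM analysis uses Dexcom G6 users only). The baseline is 14 days and the treatment session 28 days. The on-treatment rate is twice the baseline rate, the true rate ratio is 0.80, the log-normal frailty variance is 1.5, and ρ is the correlation between the periods' log frailties. An HbA1c-like covariate is in both models. The added term is log(baseline count + 0.5), with 150 replicates per scenario. Expected baseline events are rate × 14/365.25. Entries are variance of the log rate ratio, adjusted over unadjusted.

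| Baseline rate per year | Expected baseline events | No baseline event | ρ = 0 | ρ = 0.3 | ρ = 0.6 | ρ = 0.9 |
|---|---|---|---|---|---|---|
| 1 | 0.04 | 96% | 1.01 | 1.01 | 1.00 | 0.99 |
| 3 | 0.11 | 90% | 0.99 | 0.99 | 0.99 | 0.89 |
| 10 | 0.38 | 76% | 0.99 | 0.89 | 0.80 | 0.67 |

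The ρ = 0 column should be about 1.00, so departures of about 0.01 are simulation noise. Mean rate ratios were 0.785 to 0.820 without the covariate and 0.785 to 0.815 with it, so neither model shows a meaningful shift from 0.80.

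**4. Same question with baseline time below range as the covariate.** Across assumed frailty correlations, the variance ratio was about 1.00 at 1 event per year, 0.99 to 0.82 at 10 per year, and 0.97 to 0.69 at 30 per year (30 × 14/365.25 = 1.15 expected baseline events).

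**5. Interval width.** A variance reduction of 10% narrows the log-scale interval by 1 − √0.90 = 5%. A reduction of 30% narrows it by 1 − √0.70 = 16%.

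**6. Incidence rows.** A logistic simulation covered 12 scenarios (754 participants, 14-day baseline, 28-day session, 1 to 30 events per year, correlations 0.3 to 0.9). Adding baseline time below range made the standard error of the log odds ratio 0.2% to 4% larger in all 12. Power hardly moved (for example 27.3% with and without, at 10 per year and correlation 0.9), except at 30 per year with strong correlation. The covariate changes which conditional odds ratio is estimated.

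**7. Missing baselines.** Multiple imputation of baseline CGM is specified for the treatment regimen estimand on EAS1 (SAP 4.1, 4.4.1.2, 4.4.2.1). The event models sit in the safety section, which is based on the Safety Analysis Set. They keep all data and refer to Appendix 6 for missing data, and Appendix 6 interpolates only short reading gaps. By default it derives percent time below 70 mg/dL from valid periods and sessions: at least 70% of readings in a day and at least 3 valid days in a visit. A covariate built on that rule would be missing for some participants whom the event models retain.

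**The case against.** The other side has a good case, and much of it stands. The comparison is randomized and stratified by sulfonylurea use, GLP-1 RA use, HbA1c stratum and country, so it is valid without the extra term. The covariates match those of the participant-reported hypoglycemia models (SAP 4.6.3.1.1), which allows a like-for-like reading. Baseline-adjusted CGM hypoglycemia is already planned, as time below 70 and below 54 mg/dL, and those are the endpoints named in the objectives table; CGM event rates are not. Participants are insulin-naive with screening HbA1c of 7.0 to 10.5%, so baseline lows may be few. For the two Level 2 rate rows the SAP provides an empirical fallback (Appendix 9) that has no covariates, so with sparse events the choice of covariate has no effect there.

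This limits the size of the point but does not remove it. The fallback is not specified for the Level 1 or Level 2 rate row, where gain is likeliest. Matching the diary models does not explain the difference from the duration models in the same table.

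A reader might infer that the omission biases the rate ratio. Randomization and the simulated rate ratios do not support that. A reader might also infer that all six rows have needlessly wide intervals. The logistic results contradict that for the three incidence rows.

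**Conclusion.** The point holds for the post-baseline CGM event-rate models, as one of precision and consistency. The variance reduction ranges from almost nil when baseline events are rare to roughly 10 to 30% when they are frequent and well correlated between baseline and treatment. This rests on assumed rates, correlations and frailty variance, none of which the documents supply.

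Three further inferences should be resisted. The linear-model sample equivalents (4%, 14%, 33%) are not established for these models. The multiple imputation already in the SAP cannot be assumed to cover a missing baseline here. Nothing in the primary or key secondary results, the sample size or the error control is affected, because SAP 2.1 makes no multiplicity adjustment for safety assessments.

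**What to change.** In SAP 4.6.3.1.2, for the on-treatment and post-treatment negative binomial rate rows, and the Level 1 or Level 2 row above all:

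- Add one baseline CGM hypoglycemia covariate, for example transformed percent time below 70 mg/dL or the baseline event rate. Derive it from all baseline CGM data, so that it matches the data these models keep.
- Keep baseline HbA1c. Leave the baseline-session row unchanged.
- State, for these models, how a missing baseline session is handled, for example a missing indicator or single imputation.

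For the logistic incidence rows the same covariate is optional. If used, it must be prespecified, and the result is better reported as a standardized risk difference.

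The cost is SAP wording and a little extra derivation. Appendix 6 already plans an all-data sensitivity analysis for selected CGM parameters, so part of the programming may exist. The downside is a changed conditional odds ratio if the term is also applied to the logistic rows. If the SAP can no longer be changed before unblinding, report the adjusted rate model as a labeled sensitivity analysis.

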The average duration, incidence, event rate of the Level 1 or 2 and Level 2 hypoglycemia episodes will be analyzed for each CGM session. The average duration will be calculated by dividing the sum of the duration of individual episodes during the given CGM session by the number of episodes, and used in the analysis.

The hypoglycemia event rate (events/participant/year) will be calculated by dividing the number episodes by the number of CGM days \times 365.25 days.

The duration (minutes) for a day = the time of last CGM value - the time of the 1st CGM value - the sum of intervals that are >15 minutes within each CGM day.

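### CGM episode duration does not exist for a session without episodes, yet the SAP uses baseline duration as a covariate and gives no rule for participants who had no lead-in episode

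*SAP*

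**What the plan says.** SAP 6.6.2 (Hypoglycemic Episode) obtains the analysed value by "dividing the sum of the duration of individual episodes during the given CGM session by the number of episodes". A Level 2 episode needs glucose below 54 mg/dL for at least 15 consecutive minutes. A Level 1 or 2 episode needs the same below 70 mg/dL.

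The last three rows of the table in SAP 4.6.3.1.2 set out the duration models:

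- Treatment sessions (Weeks 0-4, 8-12, 22-26, 48-52): an MMRM with treatment, strata, time and treatment-by-time, "and baseline duration as a covariate".
- Weeks 0-52 combined: "ANCOVA model will include treatment, strata and baseline duration".
- Baseline and post-treatment sessions: "ANOVA models only include treatment".
- Level 2 episodes, and Level 2 episodes ending at 70 mg/dL or above: "Same models as for Level 1 or Level 2 hypoglycemic events".

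On missing data the section says "Missing data will be handled as described in" Appendix 6. That appendix deals with gaps in sensor readings, for example "Glucose reading intervals >15 minutes will be treated as missing data and not be counted in the length of the analysis periods", and with episodes cut short by a gap or by the end of a session. It has no rule for a session with complete readings and no episode.

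**The concern.** The variable is a ratio whose denominator is the number of episodes. With no episodes it is 0/0: the value is not unobserved, it does not exist. A model with this quantity as a baseline covariate can use only participants who have it, unless the plan gives another coding.

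Baseline is a 2-week CGM session in people who have not yet started insulin, with screening HbA1c of 7.0% to 10.5% (Protocol 5.1). The treatment sessions last 4 weeks each. A participant with no lead-in episode and several on-treatment episodes has a usable outcome and no covariate, so fitting the stated model discards informative on-treatment data. How long low-glucose episodes last is a natural question for an insulin with a half-life of about 17 days (Protocol 6.8.4), so these results are likely to be read.

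**Working it through.** The plan gives no sample size, power or expected N for the duration analysis, so there is no stated figure to reproduce. The check has three parts.

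**1. Does any rule supply a baseline value?**

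- SAP 6.6.2: none for zero episodes.
- SAP 6.6: covers gaps between readings only.
- SAP 4.1, table of baseline definitions: multiple imputation of a missing CGM baseline appears in the treatment regimen row. The efficacy-estimand MMRM row has none. Imputation would in any case supply a length for episodes that did not occur.
- SAP 4.4.2.2 sends CGM-based safety measures to 4.4.2.1, whose MMRM rule requires a baseline and at least one post-baseline observation. That points toward exclusion.

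No rule was found. Default complete-case handling of a missing covariate removes the participant.

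**2. Upper bound on participants entering the MMRM or the 0-52 week ANCOVA**

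Inputs: 888 randomized (SAP 5), and an assumed share p with at least one baseline episode of the relevant type. The documents do not give p.

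Maximum N = 888 × p, over both arms:

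| Assumed p | 888 × p | Maximum N |
|---|---|---|
| 2% | 17.8 | 18 |
| 5% | 44.4 | 44 |
| 10% | 88.8 | 89 |
| 20% | 177.6 | 178 |
| 40% | 355.2 | 355 |

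These are ceilings for two reasons. Each participant also needs an on-treatment episode in at least one session, and 888 exceeds the main CGM population because Libre users in China are analysed separately (SAP 1.2, 3).

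**3. Illustration of the data lost**

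One dataset of 888 was simulated per row. Baseline counts were Poisson with mean exp(m + u), and on-treatment counts Poisson with mean exp(m + 1.5 + u + 0.3 × arm), where arm is 0 or 1 and u is a standard normal participant effect. Episode lengths were gamma with mean 40 minutes. The values of m, from -4 to -1, and all other settings are assumptions.

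| Share with baseline episode | Share with on-treatment episode | N with baseline duration | N without it | SE with (min) | SE without (min) |
|---|---|---|---|---|---|
| 2.7% | 13.0% | 11 | 115 | 11.77 | 5.46 |
| 8.6% | 28.9% | 41 | 257 | 10.21 | 3.56 |
| 16.3% | 51.0% | 107 | 453 | 3.98 | 2.33 |
| 34.8% | 75.8% | 271 | 673 | 2.03 | 1.49 |

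In each row the covariate removes more than half of the participants who have an on-treatment duration (for example, 673 - 271 = 402 of 673 in the last row). Even without the covariate, N equals only the number with an on-treatment episode. That second restriction comes from the outcome definition.

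**The case against.** The strongest reply is that exclusion is inferred. The SAP nowhere says that a zero-episode session is set to missing here, and 4.6.3.1.2 states that the analysis takes in all data. A programmer could code such sessions as 0 minutes and keep everyone. This stands in part: the documents leave the handling open, and complete-case loss is the likely default rather than a written instruction. Coding the outcome as 0, however, would change mean episode length into a mixture of incidence and length, which 6.6.2 does not define. The two readings give different populations and different estimates.

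Three stronger readings are tempting and are not supported.

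- *Only a handful of participants can remain.* No baseline CGM episode rate is given. Rarity is plausible for Level 2. It is less clear for Level 1 or 2, because sulfonylureas are allowed and HbA1c may be as low as 7.0% (Protocol 5.1). If those episodes are more common, fewer participants are lost. Nor should the bound be reduced by the chance of an episode in one session, because the MMRM uses four treatment sessions and the ANCOVA combines them.
- *The covariate breaks randomization.* A lead-in episode precedes randomization. Restricting on it costs numbers and generalizability, but does not by itself bias the arm comparison. Conditioning on an on-treatment episode can, and removing the covariate does not cure that.
- *The trial lacks a sound CGM comparison of low glucose.* Time below 54 and below 70 mg/dL are named secondary endpoints (SAP 1.1), derived in 6.6.1 and compared between arms under 4.4.2.1. CGM episode incidence and rate use no baseline duration.

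**Conclusion.** The concern holds for the MMRM and the 0-52 week ANCOVA of all three CGM duration endpoints. As specified, with ordinary complete-case handling, these models exclude every participant without a lead-in episode of the relevant type. The ceiling is 44, 89 or 178 of 888 if 5%, 10% or 20% have one. Those percentages are assumptions, and the loss is smaller where baseline episodes are more common. The baseline and post-treatment ANOVAs do not carry the covariate.

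A second, separate limit applies with or without the covariate. The outcome exists only for participants with an on-treatment episode, which treatment can affect, and the MMRM would treat episode-free sessions as missing responses. An arm that prevents short episodes could therefore appear to have longer ones.

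The scope is modest. CGM episode duration is not among the listed objectives and endpoints (SAP 1.1) and has no multiplicity control (SAP 2.1). A reader might infer that the primary, key secondary or main hypoglycemia results are compromised. They are not, because none of those analyses uses baseline duration.

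**What to change.** In SAP 4.6.3.1.2 and 6.6.2:

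1. State that average duration is undefined for a session with no episode, and how such sessions are handled.
2. Remove baseline duration from the MMRM and the 0-52 week ANCOVA. Alternatively, replace it with a had-a-baseline-episode indicator plus baseline duration set to 0 when there was none. Either choice keeps the on-treatment data of participants without a lead-in episode.
3. Report the number of participants analysed per arm for each duration model.
4. Label the duration results as descriptive among participants with episodes.
5. Rest between-arm inference on time below 54 and below 70 mg/dL and on CGM episode incidence and rate, all already planned. The planned listing of Level 2 episodes longer than 360 minutes can stay.

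The cost is SAP wording and a small programming change, with no new data. What is given up is the inferential use of the duration comparison, which becomes descriptive.
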